6.5 Significance Level

Unless otherwise noted, all statistical analyses will be conducted with a significance level (α) of 0.05 and utilize two-sided testing.

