For the first criterion above, the test group will need to have less than 6%/ptyr cumulative rate of the three events for the study to reach significance with a randomized patient population of between 150 and 250 per group followed for between 5 and 6.7 years at a statistical power of 80% with type I error of 0.05 and a maximum allowable difference between groups of 1.5%. It is expected that each of 50 centers will be able to enroll an average of 30 patients into the study balanced to provide adequate population in each sub-group, providing sufficient patient-years to test the hypothesis, which under the above conditions is around 1000 as shown in Table 1. Thus the study has 200 patients per group in AVR high risk with an average of 5 years of follow-up, or alternatively 150 patients in AVR low risk averaging 6.7 years of follow-up and and up to 250 MVR averaging 4 years of follow-up, providing the approximately 1000 patient-years per group estimated to meet hypothesis.

For the second criterion above, the established rates are the objective performance criteria (OPC) given in the FDA guidance document ⁽¹⁾. The adverse event rates for which OPCs are established include the primary endpoints of thrombosis, thromboembolism and bleeding and the secondary endpoints of paravalvular leak and endocarditis as listed below:

% per valve year (R_A)
0.8
3.0
3.5
1.5
1.2
1.2

In the comparison to OPCs for each adverse event, the null hypothesis being tested is that the true adverse event rate for each test group is equal to or greater than twice the acceptable rate. Rejecting the null hypothesis would conclude that the rate for the test groups is less than two times the acceptable rate. The null and alternative hypotheses can be written as:

Null hypothesis:	$R \ge 2R_A$
Alternative hypothesis:	$R < 2R_A$

Table 1

Sample Size Estimation for On-X Trial LD Therapy vs. Control

The sample size estimation is based on one-sided proportion test, which tests that the incidence rate of thrombosis, thromboembolism and hemorrhage in the LD therapy groups are at least as low as the control groups.

				Maximum Allowable	
Type I Error	Statistical	Expected	Expected	Difference	Needed
(One-sided	Power	Proportion	Proportion	between Two Groups	Patient
Test)		In Control	In Low Dose	to Declare Non-inferiority	Years
		Group	Group		
0.05	80%	7.3%	4.5%	2.0%	309
			5.0%	2.0%	398
			6.0%	2.0%	719
			7.3%	2.0%	2112
			4.5%	1.5%	381
			5.0%	1.5%	504
			6.0%	1.5%	992
			7.3%	1.5%	3739

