			4.5%	1.0%	483
			5.0%	1.0%	663
			6.0%	1.0%	1461
			7.3%	1.0%	8388
0.025	80%	7.3%	4.5%	2.0%	393
			5.0%	2.0%	506
			6.0%	2.0%	914
			7.3%	2.0%	2682
			4.5%	1.5%	484
			5.0%	1.5%	641
			6.0%	1.5%	1260
			7.3%	1.5%	4748
			4.5%	1.0%	613
			5.0%	1.0%	842
			6.0%	1.0%	1856
			7.3%	1.0%	10650

Where R is the observed event rate and R_A is the corresponding OPC. FDA's guidance document estimates that 800 patient years are required to test this hypothesis assuming 95% confidence, 80% power and an annual attrition of 5%. This amount of trial experience is consistent with the requirements of the first criterion shown in Table 1 indicating that a patient group of 200 followed for 5 years average or 150 followed for 6.7 years average will be adequate for both purposes.

E. Center Participation

The principal investigators selected will be responsible for fulfilling the clinical trial requirements that are outlined in this investigational plan. The investigational center should have the necessary resources to allow the investigator to adhere to all clinical trial requirements. The following criteria will be used to select centers and investigators for participation in this clinical trial:

- Expertise in clinical areas relevant to the On-X heart valve LD therapy clinical trial. This includes an extensive background in cardiovascular surgery and management of patients with prosthetic heart valves, and prior experience in conducting clinical studies on prosthetic heart valves.
- Appropriate and sufficient personnel should be available to obtain and report data as required by the investigational plan. There should be an investigational group at each center consisting of at least: the investigator (a cardiovascular surgeon); co-investigators, who will also implant the study valve; and a center study coordinator to manage, organize and coordinate the routine activities of the clinical trial.
- Appropriate and sufficient patient population should be available to meet the implant schedule requirements for aortic and mitral prostheses.
- Access to a hospital and/or clinic having the equipment necessary to perform the clinical trial.
- Willingness to comply with all aspects of the clinical trial as described in the investigational plan. This includes collection of complete and accurate data in a timely manner according to the prescribed patient follow-up schedule. Additionally, investigators should be accessible to their support staff, and sponsor and monitor personnel.

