The primary study endpoints are the rates of occurrence of valve thrombosis, thromboembolism, all major and minor bleeding events whether or not related to drug therapy, reoperation, explant and death. Other valve related adverse events including endocarditis, hemolysis, hemolytic anemia, paravalvular leak and structural and non-structural dysfunction are secondary endpoints. All events shall be as defined by the AATS/STS guidelines ^[2] for reporting valve study results.

Effectiveness -

Effectiveness endpoints are also secondary endpoints and shall be New York Heart Association (NYHA) functional classification and the echocardiographic hemodynamic parameters of peak and mean gradient and effective orifice area (EOA). Echocardiographic exams shall also evaluate indexed EOA, performance index, cardiac output, cardiac index and amount and location of any valvular regurgitation.

B. Follow-up Regime and Intervals

The intent of the study design is to treat mechanical valve patients with less aggressive anticoagulation. The control group drug regimes are those from the recommendations for mechanical valves of the ACCP^[3] and the AHA/ACC^[4], while test group regimes are either a clopidogrel/aspirin mix for low risk aortic patients or reduced Coumadin to just below the present recommendations but with aspirin added. Patients will be maintained on Coumadin/aspirin beginning immediately postoperatively, with heparin used from operation until INR target is reached. Randomization and transfer to test group will occur at the 3-month visit. INR control will be accomplished using home monitoring with the system provided by QAS or in Italy with systems as provided within the processes used in medical care there. The patient in consultation with his/her physician will also make drug dosage adjustments.

Patients will be followed at 3 months, 6 months and 1-year, then annually thereafter until the study is completed when the patient groups reach sufficient patient-years experience at up to 8-years of follow-up for any individual patient and at least 1-year follow-up for all patients. Visits will be scheduled within 1-month of the appropriate anniversary. Follow-up will be conducted by physician visit.

C. Investigational Procedures

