2.3 Study Endpoints

2.3.1 Safety

The primary study endpoints are the binary measures of occurrence or not of valve thrombosis, thromboembolism (TE), all major and minor bleeding events, whether or not related to drug therapy, reoperation, explant and death. The sum of all TEs (including valve thrombosis events) and major bleeding is used as the primary decision criterion for the primary endpoints.

Secondary safety study endpoints are other valve related adverse events (AEs) including the occurrence or not of endocarditis, hemolysis, hemolytic anemia, paravalvular leak and structural and non-structural dysfunction. All events shall be as defined by the AATS/STS guidelines [Akins CW, Miller DC, Turino MI, et al] for reporting valve study results.

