4. SAMPLE SIZE CONSIDERATIONS

The study is expected to test the safety of low dose (LD) therapy for anticoagulant therapy in On-X valve patients with LD therapy consisting of the use of Coumadin® in combination with aspirin or the use of antiplatelet therapy alone. The sample size for this study was designed as a non-inferiority study requiring only that LD therapy is not inferior to standard Coumadin®/aspirin treatment. It was necessary for the sample size calculation to assume an acceptable event rate for the primary endpoints of thromboembolism, thrombosis and bleeding events derived by summing the FDA OPC's. The incident rate of the sum of these three events needs to be at least as low as the OPC sum, 7.3%.

The test group will need to have less than 6%/ptyr cumulative rate of the three events for the study to reach significance with a patient population of 200 per group followed for 5 years at a statistical power of 80% with type I error of 0.05 and a maximum allowable difference between groups of 1.5%.

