9. SAFETY ANALYSIS

9.1 Primary Analysis

The primary study endpoints are the binary measure of occurrence or not of valve thrombosis, thromboembolism, all major and minor bleeding events whether or not related to valve, reoperation, explant and death. Additionally, the sum of all TEs (including valve thrombosis events) and major bleeding will be included with the primary endpoint analyses.

For each of these binary endpoints, a Kaplan-Meier (KM) life table will be fitted and used to compare each valve treatment group and its control group. The KM analysis will adjust for select risk factors

including age and gender. In addition, the linearized rates as well as overall percentages of occurrences will be included in summary tables. Comparisons of overall percentages between each valve treatment group and its control will be made using a chi-square test or Fisher's exact test as appropriate. Linearized rates will be analyzed for differences between treatment and control groups with relative risks and 95% confidence intervals.

Analyses of mitral valve subjects will also be stratified by location (North America versus Italy) in the summary tables.

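### The non-inferiority comparison is sized at one-sided 0.05, but the SAP prescribes two-sided 0.05 and 95% intervals; judged that way, power at 1000 patient-years per group is about 70%, not 80%

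*SAP*

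**What the plan says.** **Protocol, section II.D.** Above Table 1 the protocol states: "The sample size estimation is based on one-sided proportion test". The table gives patient-years for one-sided 0.05 and for one-sided 0.025. The text adopts a row from the 0.05 block (control 7.3%, low dose 6.0%, margin 1.5%, 80% power: 992) and describes the requirement as one "which under the above conditions is around 1000 as shown in Table 1". It then concludes that "a patient group of 200 followed for 5 years average or 150 followed for 6.7 years average will be adequate for both purposes". Section III.B ends the study when the groups reach "sufficient patient-years experience at up to 8-years of follow-up for any individual patient".

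**SAP, section 4.** The design is again non-inferiority, with 200 patients in each group and 5 years of follow-up. The error level and margin read: "at a statistical power of 80% with type I error of 0.05 and a maximum allowable difference between groups of 1.5" percent. The word one-sided is not carried over.

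**SAP, section 6.5.** Unless otherwise noted, "all statistical analyses will be conducted with a significance level (α) of 0.05 and utilize two-sided testing".

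**SAP, section 9.1.** Linearized rates are compared "with relative risks and 95% confidence intervals", and overall percentages by chi-square or Fisher's exact test. The section names no margin, no one-sided test and no 90% interval.

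**SAP, section 2.3.1.** The sum of thromboembolism (including valve thrombosis) and major bleeding "is used as the primary decision criterion for the primary endpoints".

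**The concern.** The 80% power belongs to a one-sided 0.05 test of the rate difference, which corresponds to the upper limit of a two-sided 90% interval. The SAP never prescribes that test. The only error level and interval it does prescribe are two-sided 0.05 and 95%. Non-inferiority looks at one limit of the interval, so a 95% interval means one-sided 0.025.

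Two things are at stake. The stated power would be too high for the analysis as written. And the same result could pass with one interval and fail with the other, with nothing in the SAP to settle which counts. For a safety claim about reduced anticoagulation, that choice should not be left until the data are known.

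**Working it through.** **Inputs** (Protocol II.D and Table 1, repeated in part in SAP 4): control rate 0.073, low-dose rate 0.060, margin 0.015, power 80%, equal groups, about 1000 patient-years per group. The event is harmful, so the distance from the margin is 0.015 + (0.073 − 0.060) = 0.028.

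**1. Reproduce Table 1.** With an unpooled normal approximation, treating each patient-year as a binomial trial:

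- v = 0.073 × 0.927 + 0.060 × 0.940 = 0.12407
- n = (z_α + 0.842)² × v / 0.028²
- One-sided 0.05 (z = 1.645): n = 978, against 992 in the table
- One-sided 0.025 (z = 1.960): n = 1242, against 1260 in the table

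Both are within 1.5% of the table, so the method is close to the one used. On the table's own figures, the move from 0.05 to 0.025 costs 1260/992 = 1.27, or 27% more patient-years.

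**2. Power at 1000 patient-years per group.** SE = √(0.12407/1000) = 0.01114, and power = Φ(0.028/SE − z).

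| Calculation | 90% interval (one-sided 0.05) | 95% interval (one-sided 0.025) |
|---|---|---|
| Binomial variance | 80.8% | 71.0% |
| Scaled to Table 1's own N | 80.3% | 70.4% |
| Poisson variance, v = 0.073 + 0.060 | 78.3% | 68.0% |

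The scaled row uses Φ((z_α + 0.842) × √(1000/N) − z_α), with N = 992 or 1260.

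**3. What must be observed to pass** (low dose minus control):

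- 90% interval: 1.5 − 1.645 × 1.114 = −0.33 points
- 95% interval: 1.5 − 1.960 × 1.114 = −0.68 points

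Under the planning rates, the chance of landing between these is 0.808 − 0.710, about 10%. This is the power loss in another form: the share of trials in which the interval level alone decides.

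**4. What restores 80% power with a 95% interval on the difference.**

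- At 1000 patient-years per group, a true low-dose rate of about 5.7%. At 5.71% the distance is 0.0309, v = 0.067671 + 0.0571 × 0.9429 = 0.12151, SE = 0.01102, and Φ(0.0309/0.01102 − 1.960) = 80%.
- At a true 6.0%, 1260 patient-years per group (Table 1). That is 1260/200 = 6.3 years on average, 1260/250 = 5.0 years, or 1260/150 = 8.4 years. The last exceeds the 8-year limit on any one patient's follow-up.

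**5. On the SAP's relative-risk scale.** The documents give no ratio margin. Assuming, for illustration only, that the margin converts to (7.3 + 1.5)/7.3 = 1.205, the log rate ratio has SE = √(1/60 + 1/73) = 0.174. Power is Φ((ln 1.205 − ln(0.060/0.073))/0.174 − z): about 59% with a 95% interval and 71% with a 90% interval.

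**The case against.** The strongest reply is that SAP 6.5 leaves room for exceptions and SAP 4 may supply one. It repeats the non-inferiority design, 0.05, 80% power, the 1.5-point margin and 200 patients for 5 years, and with 7.3% and 6% these figures match only the one-sided 0.05 row of Table 1. The intent can be inferred from that. But SAP 4 does not state sidedness, and SAP 9.1 still specifies 95% intervals, so the SAP alone leads the analyst to the stricter level. Protocol section III.H sets no level either.

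Four other points stand in part:

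- The 70% depends on a rule that neither document states, namely a 95% interval on the absolute difference set against 1.5 points. That is right; the missing rule is part of the defect.
- Table 1 tabulates both levels and its figures are sound. The fault is a mismatch between the adopted row and the SAP, not a miscalculation.
- The protocol asks for less than 6%, so 6.0% is the least favourable planning value. With the formula above and a 95% interval, power is about 85% at a true 5.5% and 94% at 5.0%. The stated design figure is nonetheless tied to 6.0%.
- The group of 150 is low-risk AVR, which the protocol says is closed, so the 8.4-year figure has little practical weight now. For 200 or 250 patients the required averages stay under 8 years, and the protocol ends the study on accumulated experience, not at a fixed 1000.

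The two-sided reading is also the conservative one and does not raise the risk of a false claim of non-inferiority.

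**Conclusion.** The concern holds. The protocol's 80% power applies to a one-sided 0.05 test that the SAP does not prescribe. Under the only error level and interval the SAP does prescribe, applied to the sized difference, power at 1000 patient-years per group is 70–71% (68% with Poisson variance), and Table 1's own requirement is 1260 patient-years. These figures assume 7.3% against 6.0%, a 1.5-point margin, equal groups and the three-event sum used for sizing. They have not been worked out for the SAP 2.3.1 criterion of thromboembolism plus major bleeding. The loss shrinks quickly if the true low-dose rate is below 6.0%. The consequence is overstated power and an undecided rule, not a higher error rate, so this should be corrected but does not undermine the design.

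**What to change.** In SAP 4, 6.5 and 9.1, state that the primary non-inferiority comparison is judged on the absolute difference in linearized rates against 1.5% per patient-year, and set its error level in one of two ways:

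- **(a)** one-sided 0.05, using the upper limit of a two-sided 90% interval, as the adopted row of Table 1 assumes; or
- **(b)** keep the 95% interval and restate power as about 70% at 1000 patient-years per group under 7.3% against 6.0%, or equivalently say that 80% power needs a true low-dose rate of about 5.7%. Label the figure as applying to the sized three-event sum.

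Keep two-sided 0.05 for all other analyses. The cost is two or three sentences in the SAP and, under (b), a lower stated power. No patients are added.

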6.6 Statistical Notation and Methodology

Unless stated otherwise, the term "descriptive statistics" refers to the number of subjects (n), mean, median, standard deviation (SD), minimum, and maximum for continuous data and frequencies and percentages for categorical data. Unless otherwise noted, all data collected during the study will be included in data listings and will be sorted by treatment group, subject number and then by date/time within each subject number.

7. DATA HANDLING METHODS

7.1 Missing Data

7.1.1 Date Values

For the purposes of analysis, imputation of incomplete or missing dates may be performed (i.e. determination of treatment-emergent/post-operative status).

For incomplete or missing dates, the date components will be imputed with the most conservative value possible (i.e. first day of the month if day is missing in a start date or earliest date in a visit window for a missing value).

7.1.2 Non-Date Values

Every effort will be made to obtain required data at each scheduled evaluation from all subjects who have been enrolled. There will be no imputation for missing data.

7.2 Visit Windows

Study periods will be windowed as applicable according to the following:

- Pre-operative
- Operative
- Discharge
- Follow-up:
 - o 3 months + 1 month, 0 months
 - o 6 months ± 2 weeks
 - o 1, 2, 3, 4, 5 or 5+ yrs (± 1 month)
- Reoperation
- Off schedule

Visits will be presented according to the nominal visit as obtained from the CRF and/or schedule of time and events (section 3.2). If multiple on-schedule assessments are collected for the same characteristic and fall within the same nominal visit window, then the latest value will be used for summary presentation. For off-schedule assessments, those used in the calculation of linearized rates and event

counts will be included in the summary presentations but excluded for those analyzed specifically for on-schedule visits (i.e. NYHA, anticoagulant therapy, etc.).

All assessments, both on-schedule and off-schedule, will be included in the data listings.

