Suture Interrupted Technique:	Suture Interrupted Pledgeted Everting Mattress Noneverting Technique: Continuous Other, specify:				
Crossclamp time:Minutes					
Cardioplegia:	$Cold$ \Box $Warm$ \Box Bo	th			
	Antegrade Retrograde	Both			
Intraoperative Drugs: Heparin □ Yes □ No					
Apro	$_{\rm otinin}$ \Box $_{\rm Yes}$ \Box $_{\rm No}$				
Intraoperative Adverse Events: Ves No (If Yes, complete below.)					
Prolonged Hypotension Yes N	o Difficulty Resta	arting Rhythm 🗌 Yes 🗌 No			
Excessive Bleeding \Box Yes \Box N	o Difficulty Wear	ning from Bypass \Box Yes \Box No			
Cardiac Tamponade 🛛 Yes 🖓 N	o Study Valve Ex	planted Yes No			
Cardiac Arrest $\Box_{\text{Yes}} \Box_{\text{N}}$	o Death	\square_{Yes} \square_{No}			
Other 🗆 Yes 🗆 M	lo If Yes, explain:				
Valve Orientation: Check the most accurate valve orientation description below based upon the direction of the valve axis. Mitral: Anatomical Other, describe:					
Aortic: LC/RC commissure RC/NC commissure NC/LC commissure					
Investigator Signature:	D	ate (m/d/y)://			

Institution:	MCRI On-X [®]	Patient Initials	
Investigator:	Anticoagulation Study CRF 3	Patient No.	
Visit Date (m/d/y)//	_ □ Early PostOpe	rative/Discharge	
	\Box Interim (3	or 6 month)	
	Annual (year) (12 + 2	month interval)
	└ Off Schedule		
Group: Randomized to: Treatm	nent Control		
Patient StatusImage: Missed Follow(If follow upImage: Lost to FollowOff Schedule)Efforts toImage: Missed FollowAdverse Event	ow Up Visit. Reason, ow Up: o Contact and Results: ent (Complete Complications I	Form CRF 4)	
Type of Examination: Office/Outpaties	nt 🗌 Hospital 🗌 Telephone	□ Other	
NYHA Class: I I II		Unknown	
Cardiac Rhythm:	Regular		
Atrial Fil	prillation Other, specify:		
Anticoagulant INone	U Warfarin/Cour	nadin	
	rel Heparin		
Aspirin	□ Other		
INR Blood Collec	tion Date (m/d/y):/	_/(closest to	date of visit)
New Complications: (Since last follow up) Yes No (C	omplete complicatio	n form, CRF 4)
Echo Completed (m/d/y)	Attach CRF 6 and send echo, a	pplicable only at 1, 2	3 and 5 yr follow-up.

Investigator Signature: _____ Date (m/d/y): ____/____

Institution:	MCRI On-X [®] Low Dose	Patient Initials	
Investigator:	Anticoagulation Study CRF 4		
	Complications 1 of 2	Patient No.	
Start Date (m/d/y)://	Stop Date (m/d/y):	or \	
Duration: Week	s Days Hours	Minutes	
Etiology:			
Complication Type (check all that apply)	Complicatio	on number:	
1. Thromboembolism INeurolo	gic: 🗌 TIA 🛛 Peripheral: 🗌] Major 🔲 Cardiac: MI 🗌 Unknown	
		Minor	

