3. STUDY DESIGN

3.1 Overall Study Design and Treatment Groups

This is a longitudinal, randomized (randomization to occur at the 3 month follow-up) study comparing the On-X valve on low dose anticoagulation (test group) to concomitant control groups of On-X valves receiving standard Coumadin®/aspirin therapy, and also to FDA objective performance criteria (OPC) [ISO 5840:2005 Cardiovascular implants – Cardiac valve prostheses and Draft guidance for industry and FDA staff – Heart valves – Investigational Device Exemption (IDE) and Premarket Approval (PMA) applications, January 20, 2010]. It is a multicenter study consisting of 40 centers in the United States enrolling no more than 1200 patients (200 in each of 6 groups)

18 April 2011

[figure not shown]
Overall Schedule of Time and Events 3.2

5+ Year 5 Year 4 Year 3 Year 2 Year 1 Year 6 Month 3 Month Discharge Operation Preoperation

Form/Data

CRF 1

Card

Death

Required only if needed Required data Not applicable

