10. EFFICACY ANALYSIS

Effectiveness endpoints are all secondary endpoints and are the New York Heart Association (NYHA) functional classification score and the echocardiographic hemodynamic measures of peak and mean gradient and effective orifice area (EOA).

Additional echocardiographic assessments including the indexed EOA, MOA by the pressure half-time method, performance index, cardiac output, cardiac index and amount and location of any valvular regurgitation will be included in the efficacy analyses.

All secondary endpoints and assessments will be summarized with descriptive statistics by treatment group and visit. Mitral valve subjects will also be stratified by location. To assess treatment group differences, quantitative endpoints will use a two-sample Z-test (or t-test for small samples), ordinal endpoints will use a Wilcoxon rank-sum test, and nominal endpoints will use the chi-square test of association.

All data will be included in data listings.

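### SAP 7.2 puts every annual visit after year 5 into one undated 5+ category, so late NYHA summaries can mix years 6, 7 and 8

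*SAP*

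**What the plan says.** **Windows.** SAP 7.2 lists the annual follow-up windows as "1, 2, 3, 4, 5 or 5+ yrs (± 1 month"). The column heads of the SAP 3.2 schedule, which the PDF reading gives in reverse order, also end at 5+: "5+ Year 5 Year 4 Year 3 Year 2 Year 1 Year 6 Month 3 Month Discharge Operation Preoperation".

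**Several values in one window.** When on-schedule assessments of the same item "fall within the same nominal visit window, then the latest value will be used for summary presentation". The same section keeps all assessments, on or off schedule, in the data listings.

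**Assigning the visit.** "Visits will be presented according to the nominal visit as obtained from the CRF and/or schedule of time and events (section 3.2"). CRF 3 (Protocol Appendix A) has a box for the annual visit with its year: "Annual (year) (12 + 2".

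**Use of visits.** SAP 10 has the secondary endpoints and assessments "summarized with descriptive statistics by treatment group and visit", and compares ordinal endpoints between arms with a Wilcoxon rank-sum test. NYHA class is a named secondary endpoint.

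**Length of follow-up.** Protocol III.B sets annual visits, with "up to 8-years of follow-up for any individual patient", and the late follow-up text in III.C has the same ceiling. The opening of III.C, however, describes annual assessments to 5 years only. Protocol II.D plans mean follow-up of 5 years in high-risk AVR, 4 years in MVR and, for low risk, "150 patients in AVR low risk averaging 6.7 years of follow-up".

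**The concern.** Under an 8-year ceiling, visits at years 6, 7 and 8 are scheduled visits. If all three share one window and only the latest counts, one patient's year-6 NYHA class is summarised and tested alongside another patient's year-8 class as if both came from the same visit. Which year a patient supplies depends on entry date, survival and retention. If retention differs between arms, the 5+ comparison sets the arms against each other at different times since surgery.

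A tolerance of one month either side also needs a target date. Years 1 to 5 each have one. An open-ended category does not.

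What is at stake is how NYHA class beyond year 5 can be read, and whether two programmers working from the same SAP would produce the same table.

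**Working it through.** The documents give no figure for the share of late values left out, so there is none to reproduce. The check has three steps.

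**1. Visits that can fall in 5+.** Visits are annual and end by year 8, so the possible visits are years 6, 7 and 8, at most three per patient.

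**2. Share unused in summaries.** A patient with k visits after year 5 supplies one value, so the unused share is (k − 1)/k:

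- k = 1: 0/1 = 0%
- k = 2: 1/2 = 50%
- k = 3: 2/3 = 66.7%

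Pooled over patients, the share is (visits − patients)/visits. For assumed mixes of patients whose last visit is at year 6 : 7 : 8:

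- 3:2:1 gives 10 visits in 6 patients, 4/10 = 40%
- 1:1:1 gives 6 visits in 3 patients, 3/6 = 50%
- 0:1:1 gives 5 visits in 2 patients, 3/5 = 60%

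The full range is 0% (all stop at year 6) to 66.7% (all reach year 8).

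**3. Illustration at the planned means.** The documents give only the means, a 1-year minimum and an 8-year maximum. Assume follow-up T is uniform on an interval (a, b) with the planned mean and inside those limits. Then P(T ≥ t) = (b − t)/(b − a), and the unused share is [P(7) + P(8)]/[P(6) + P(7) + P(8)].

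| Group | Mean | Interval (years) | P(6) | P(7) | P(8) | Unused |
|---|---|---|---|---|---|---|
| AVR high risk | 5 | 2 to 8 | 0.333 | 0.167 | 0 | 0.167/0.500 = 33% |
| AVR low risk | 6.7 | 5.4 to 8 | 0.769 | 0.385 | 0 | 0.385/1.154 = 33% |
| MVR | 4 | 1 to 7 | 0.167 | 0 | 0 | 0% |

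If a visit may take place one month early, t is replaced by t − 1/12:

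| Group | P(6) | P(7) | P(8) | Unused |
|---|---|---|---|---|
| AVR high risk | 0.347 | 0.181 | 0.014 | 0.194/0.542 = 36% |
| AVR low risk | 0.801 | 0.417 | 0.032 | 0.449/1.250 = 36% |
| MVR | 0.181 | 0.014 | 0 | 0.014/0.194 = 7% |

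The second table also shows the mixing. In high-risk AVR, the value kept for 5+ comes from year 6 in (0.347 − 0.181)/0.347 = 48% of contributing patients, from year 7 in (0.181 − 0.014)/0.347 = 48%, and from year 8 in 0.014/0.347 = 4%. The low-risk figures give the same split.

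**Which outputs are touched.** The event endpoints, including the decision criterion in SAP 2.3.1 (thromboembolism plus major bleeding), are analysed in SAP 9.1 by Kaplan-Meier, linearized rates and overall percentages. None of these uses a by-visit value. Protocol III.C and III.D require echocardiography at years 1, 3 and 5 only. SAP 7.2 mentions anticoagulant therapy as analysed by on-schedule visit, but the display list in SAP 14.1 has no postoperative anticoagulant table. That leaves late NYHA class (Tables 14.2.2.1 to 14.2.2.3).

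**With separate windows.** Each annual window then holds one scheduled visit, so the latest-value rule leaves nothing out except true duplicates.

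**The case against.** The strongest reply is that the merging is one reading of SAP 7.2 and not a stated rule. Protocol III.B places visits within a month of each anniversary, so the tolerance makes sense if 5+ is shorthand for every later anniversary. The SAP allows the nominal visit to come from the CRF, and CRF 3 carries the year. A programmer could keep years 6, 7 and 8 apart without breaking the SAP. This is fair, but the SAP equally allows the schedule as the source, and both the schedule and the window list stop at 5+. The two permitted sources lead to different tables, and that choice should not be left to programming.

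A second reply is that the SAP dates from April 2011 and assumes 5 years of follow-up (SAP 4), for which a residual category is reasonable. That explains the wording. It does not make it fit the March 2014 protocol, which plans for longer follow-up.

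Other objections stand and limit the point:

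- The low-risk AVR arm, with the longest planned mean, has been closed (Protocol II.C), and the other groups plan means of 5 and 4 years.
- Separate windows do not cure differential retention, because the year-7 and year-8 rows will contain only those still followed.
- Testing each late year would add sparse comparisons in a SAP that makes no multiplicity adjustment (SAP 6.4).

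**Conclusion.** The point holds as a minor one. Followed as written, SAP 7.2 and 3.2 would most naturally summarise and test NYHA class from years 6, 7 and 8 as a single visit whose window has no target date. The share of post-year-5 values left out of those summaries lies between 0% and 67%. It is about a third in AVR and 0% to 7% in MVR under the uniform follow-up assumed above. These shares rest on assumed distributions; only the per-patient figures of 0%, 50% and 67% follow directly from the rule.

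A reader might infer that half to two thirds of the late data are thrown away. The documents do not support that. The values leave the summaries and by-visit tests only and remain in the listings. The 50% and 67% apply to patients with two or three visits after year 5, and nothing in the plan says that most patients will have that many. Nor does the point reach the trial's main conclusion, since the primary event analyses do not use visit windows. Bias between arms is possible only if retention differs by arm, which the documents do not address.

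**What to change.** In SAP 7.2 and the SAP 3.2 schedule:

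- Replace the combined 5-or-5+ entry with years 5, 6, 7 and 8, each ± 1 month.
- State that the year is taken from CRF 3.
- Apply the latest-value rule only within a single annual window.
- Present NYHA class by year, descriptively and without a test where a late year is sparse.

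Reconcile the opening of Protocol III.C (annual assessments to 5 years) with Protocol III.B and the late follow-up text in III.C (up to 8 years), and carry the agreed maximum into the window list.

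The cost is SAP wording and a few extra table rows, some with small numbers. No new data or patients are needed.
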